## 10 STATISTICAL METHODS AND DETERMINATION OF SAMPLE SIZE

### 10.1 General Considerations

A detailed statistical analysis plan will be developed and finalized (approved with signatures) before the Blind Data Review Meeting (BDRM), and may be amended after the BDRM and before unblinding the study database if the need arises.

The statistical analysis plan will include the exact definition of endpoints and variables to be analyzed, extensive details of the statistical analysis methods to be used together with the structure of tables and figures to be included as end-of-text tables and figures as well as appended listings for the clinical study report.

All endpoints and variables will be adequately evaluated. Individual data will be listed. Data will be summarized using suitable descriptive statistics; depending on the structure of the data, either sample statistics or frequency tables will be used. Data will be analyzed by cohort and study period (Main Period and Extension Period) and might be further differentiated (e.g., by visit or by study site).

### 10.2 Determination of Sample Size

The primary efficacy endpoint will be analyzed using the multiple comparisons procedure-modelling (MCP-Mod) procedure [26-28]. A total of 175 subjects are planned to be

---

enrolled into the study (i.e., 35 subjects per cohort) to achieve at least 29 subjects per cohort available for the primary analysis of the primary efficacy endpoint.

The sample size is selected in a way that the multiple contrast test exceeds a power of 90%. With the planned sample size, the power criterion of the multiple contrast test is fulfilled because 29 subjects per cohort would yield a power of at least 90% to detect a dose-response signal if present. In this context, the HiSCR at Week 16 is assumed to be 25% in the placebo group, as shown in earlier HS studies [15], and 30%, 45%, 55%, and 60% in the active cohorts (Cohorts 2 to 5), with cumulative doses of 2000 mg, 4800 mg, 8000 mg, and 10,800 mg, respectively. A 1-sided significance level of  $\alpha = 0.025$  will be used.

Additionally, simulations were conducted to investigate the expected length of the 2-sided 90% confidence intervals (CIs) for the minimum effective dose (MED) and the median effective dose (ED50). Definitions of MED and ED50 can be found in Section 10.5. Based on the planned sample size of at least 29 evaluable subjects per cohort, wide 90% CIs can be expected for the MED and the ED50. The expected length of the 90% CIs was determined by simulations of the modelling step of the MCP-Mod procedure. To determine the true HiSCR at Week 16, a maximum possible effect for the agonist (Emax) model and a logistic model were selected, which are the same models that will be used as candidate models in the MCP-Mod procedure. A guesstimate of ED50 = 3000 was used for the Emax model and guesstimates of ED50 = 3500 and  $\delta = 1100$  was used for the logistic model.

## 10.3 Analysis Sets

*Full analysis set (FAS)*: the FAS will consist of all subjects who will receive at least 1 infusion of IMP. The analysis will be based on the cohort the subjects are randomized to (intention-to-treat principle).

*Per protocol set (PPS)*: the PPS will be a subset of the FAS and will exclude all subjects with major protocol violations that affect the evaluation of the primary endpoint of the study. Subjects who will receive treatment from a cohort that they are not randomized to for the complete treatment course until Week 16 will not be excluded from the PPS and will be analyzed based on the actual treatment they will receive.

*Safety analysis set (SAS)*: the SAS will consist of all subjects who will receive at least 1 infusion of IMP. Subjects will be analyzed according to the treatment they actually received. Actual treatment refers to the individual dosing schedule. The allocation of single subjects to the actual dosing groups will be performed under blinded conditions during the blinded data review.

Safety analyses will be based on the SAS. Efficacy analyses will be provided for the FAS and the PPS.

More detailed specifications of the analysis sets and analyses will be provided in the statistical analysis plan.

## 10.4 Endpoints

### 10.4.1 Efficacy Endpoints

The primary efficacy endpoint is the percentage of subjects with a response on the basis of the HiSCR (Section 8.2.2.2) determined at Week 16, before administration of IMP.

The secondary efficacy endpoints are:

- Percentage of subjects with a response on the basis of the HiSCR determined at Week 12, before administration of IMP

- 
- Number of subjects with flares analyzed in terms of  $\geq 25\%$  increase in AN count among subjects with a minimum increase of 2 in AN count relative to Day 1
  - Absolute values and absolute and relative change in mSS from Day 1 by time point
  - Absolute value and absolute and relative change in Patient's Global Assessment of Skin Pain (NRS) from Day 1 by time point
  - Percentage of subjects achieving, by time point:
    - At least a 30% reduction and at least 1 unit reduction from Day 1 among subjects with baseline NRS  $\geq 3$  in Patient's Global Assessment of Skin Pain (NRS30)
    - At least a 50% reduction and at least 2 units reduction from Day 1 among subjects with baseline NRS  $\geq 3$  in Patient's Global Assessment of Skin Pain (NRS50)
  - Absolute values and absolute and relative change in DLQI score from Day 1 by time point

Exploratory efficacy endpoints:

- Percentage of subjects with  $\geq 50\%$  reduction in AN count compared to Day 1 by time point
- Percentage of subjects with no increase in number of abscesses compared to Day 1 by time point
- Percentage of subjects with no increase in number of draining fistulas compared to Day 1 by time point
- Percentage of (partial) responders measured by HiSCR and HiSCR25 by time point
- Percentage of subjects with  $\geq 25\%$  relative and  $\geq 2$  absolute increase in counts, using the abscess count, the inflammatory nodule count, and the draining fistula count by time point
- Achievement of clear or minimal severity of HS-PGA among subjects with at least 2 grades of improvement (reduction) from Day 1 to each time point.

The endpoints that are evaluated by time point will be analyzed in a similar way during the Extension Period. Summary tables for the Extension Period will be grouped by HiSCR responders and non-responders.

In addition, the percentage of subjects with loss of response, defined as a loss of at least 50% of the improvement (reduction) in the AN count achieved from baseline to Week 16 [ $AN > \frac{1}{2} \times (\text{Baseline AN count} + \text{Week 16 AN count})$ ] based on the number of subjects with HiSCR at Week 16 will be analyzed for the Extension Period.

Descriptive subgroup analyses will be performed on selected efficacy endpoints. Relevant subgroups are defined by subjects with and without previous exposure to adalimumab or other biologic products, and with and without response to adalimumab or other biologic products, Hurley Stage, antibiotic treatment, and baseline demographics. The subgroup analyses will be exploratory. Details on subgroup analyses and further subgroup analyses (if deemed necessary) will be provided in the statistical analysis plan.

Other efficacy endpoints (e.g., erythema assessment, Patient's Assessment of Drainage and analgesic therapy) will be exploratory, as defined in detail in the statistical analysis plan.

---

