#### **8.2.2.9 Patient's Global Assessment of Skin Pain (NRS)**

The Patient's Global Assessment of Skin Pain (NRS) (Appendix 17.6) will be assessed by subjects every day in an e-diary from Screening through the FUV at Week 44.

The NRS will be used to assess the worst and average skin pain due to HS. Ratings for these 2 items range from 0 (no skin pain) to 10 (skin pain as bad as you can imagine).

Subjects should be instructed to respond to the items based on a recall period of the "last 24 h". They should also document any analgesic therapy in the e-diary.

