## **10.6 Demographics and Baseline Characteristics**

Baseline characteristics and demographic information (including medical/HS history and surgeries) will be summarized by cohort and overall. A baseline measurement will be defined as the latest measurement obtained prior to the first administration of IMP, if applicable.

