## 17.6 Patient's Global Assessment of Skin Pain

Please answer the questions below before you go to bed. Please mark an "X" in the box (☒) which best describes the severity of your skin pain in the last 24 hours.

1. In the last 24 hours, which number best describes your skin pain at its worst due to your HS?
	
No skin pain Skin pain as bad as you can imagine
 
▼ ▼
 
0 1 2 3 4 5 6 7 8 9 10
 
☐ ☐ ☐ ☐ ☐ ☐ ☐ ☐ ☐ ☐ ☐

--	---

2. In the last 24 hours, which number best describes your skin pain on average due to your HS?
	
No skin pain Skin pain as bad as you can imagine
 
▼ ▼
 
0 1 2 3 4 5 6 7 8 9 10
 
☐ ☐ ☐ ☐ ☐ ☐ ☐ ☐ ☐ ☐ ☐

--	---

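### The Day 1 reference for skin pain conflicts with a bedtime diary and the pre-dose baseline rule; a 7-day pre-dose mean would settle it and add precision without new data

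*Combined protocol and SAP*

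**What the plan says.** Section 10.4.1 lists among the secondary endpoints "Absolute value and absolute and relative change in Patient's Global Assessment of Skin Pain (NRS) from Day 1 by time point". The responder endpoints follow the same pattern. NRS30 is defined as "At least a 30% reduction and at least 1 unit reduction from Day 1 among subjects with baseline NRS" of at least 3, and NRS50 has the same structure with a 50% and 2-unit reduction.

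Section 8.2.2.9 says that the scale "will be assessed by subjects every day in an e-diary from Screening through the FUV at Week 44". Subjects are to "respond to the items based on a recall period of the" last 24 hours. The form in Appendix 17.6 instructs: "Please answer the questions below before you go to bed". There are two items: "The NRS will be used to assess the worst and average skin pain due to HS". Section 10.4.1 does not say which of them defines the endpoints.

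Section 10.6 defines a baseline measurement, where applicable, as the "latest measurement obtained prior to the first administration of IMP". Section 10.5.1 summarises the other continuous efficacy endpoints as changes from baseline. Section 10.1 leaves exact endpoint definitions to a statistical analysis plan, and the reviewed file contains no separate SAP text that settles the point.

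**The concern.** The first infusion is given at the Day 1 site visit. A diary entry dated Day 1 and made at bedtime therefore comes after that infusion, and its 24-hour recall covers hours on both sides of it. Taken literally, Section 10.4.1 measures change from a score that is partly post-dose. Section 10.6 would select the entry from the evening before.

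NRS30 and NRS50 combine the two terms: the reduction is counted from Day 1, while the subset is defined by baseline NRS. The reference score and the score that decides who is counted could come from different evenings.

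Two things are at stake. If the Day 1 entry is used, any very early effect is subtracted from the measured change, and the subset with a score of 3 or more is selected on a value that treatment may have touched, so the denominators could differ between cohorts. If the last pre-dose entry is used, that problem disappears, but the reference is still one evening of a variable symptom, although a run of pre-dose scores is being collected.

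**Working it through.** **1. Which entry is meant.**

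| Source | Implied reference for a bedtime diary |
|---|---|
| 10.4.1, change counted from Day 1 | Evening of Day 1, after the infusion |
| 10.6, latest value before first dosing | Evening before Day 1 |
| 10.5.1, change from baseline | As 10.6 |
| 10.4.1, NRS30/NRS50 | Both terms in one definition |
| 7.2, NRS listed among assessments before dosing | Unclear, because it is listed only as a daily e-diary item |

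The DLQI, HADS, SF-36v2 and EQ-5D-5L must be completed at the site before other assessments (8.2.2.10 to 8.2.2.13). The NRS has no such rule.

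**2. How much of a Day 1 entry would be post-dose.** The documents give no clock times. Assume bedtime at 22 to 23 h. The post-infusion share of the recall is (bedtime − end of infusion)/24.

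- Infusion ends at 9 h: 13/24 to 14/24, or 54% to 58%.
- Infusion ends at 12 h: 10/24 to 11/24, or 42% to 46%.
- Infusion ends at 16 h: 6/24 to 7/24, or 25% to 29%.

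This is a share of the recall period, not a bias. The bias also depends on how much pain changes within hours of one infusion, which the documents do not state.

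**3. What pre-dose data exist.** Screening takes place 28 to 10 days before first dosing (7.1) and the diary starts then, which gives about 10 or more pre-dose evenings. A 7-day window also lies inside the 14-day analgesic washout (5.8.2.3).

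**4. Precision.** The plan gives no SD, correlation or power figure for the NRS, so there is no figure to reproduce. The inputs are assumptions. ICC is the share of single-day variance due to the subject's stable level in that week, and r is the correlation of that level between baseline and the later time point. With single-day variance set to 1:

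- Single day at both ends: 2(1 − ICC·r).
- 7-day mean at both ends: 2(ICC + (1 − ICC)/7 − ICC·r).
- Fractional reduction, both ends averaged: (6/7)(1 − ICC)/(1 − ICC·r).
- Fractional reduction, baseline only: exactly half of that.

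Example with ICC 0.6 and r 0.6: single day 2(1 − 0.36) = 1.28; both ends 2(0.6 + 0.0571 − 0.36) = 0.594; reduction 1 − 0.594/1.28 = 54%.

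| ICC | r | Both ends averaged | Baseline only |
|---|---|---|---|
| 0.6 | 0.4 | 0.343/0.76 = 45% | 23% |
| 0.6 | 0.6 | 0.343/0.64 = 54% | 27% |
| 0.7 | 0.4 | 0.257/0.72 = 36% | 18% |
| 0.7 | 0.6 | 0.257/0.58 = 44% | 22% |
| 0.8 | 0.4 | 0.171/0.68 = 25% | 13% |
| 0.8 | 0.6 | 0.171/0.52 = 33% | 16% |
| 0.9 | 0.4 | 0.0857/0.64 = 13% | 7% |
| 0.9 | 0.6 | 0.0857/0.46 = 19% | 9% |

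The direction holds for any ICC below 1. The size depends on it strongly.

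**The case against.** A reader might infer that the trial has adopted a treatment-contaminated pain baseline. The documents do not support that as a settled rule. Section 10.4.1 uses Day 1 as a common label for the mSS, DLQI and lesion counts as well, and Sections 10.5.1 and 10.6 both point to a pre-dose value. Contamination follows from one reading only, and even then it is partial. This part of the objection stands. What remains is that the two sections select different evenings and nothing says which governs the diary.

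A reader might also infer that the plan prescribes a single diary day at follow-up. That comes from silence: the mapping of daily scores to time points is undefined, and a weekly average is not excluded. For the baseline, the texts are more specific. One names a day and the other the latest measurement, and neither provides for averaging.

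It is tempting to quote 25% to 54% as the cost of the Day 1 reference. That range requires averaging at both ends; averaging the baseline alone gives half. It also assumes independent daily deviations around a stable weekly level. If those deviations carry over from day to day, the gain is smaller. An analysis adjusted for baseline would also gain less from averaging the baseline alone.

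Finally, regression to the mean after selecting scores of 3 or more might be read as biasing the cohort comparison. With a pre-dose baseline the selection precedes treatment, so randomisation makes the expected regression the same in every cohort. Within-arm response rates are inflated, but between-cohort comparisons are not biased by this alone.

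The choice of 7 days and of a minimum number of entries is a convention, not something that the documents require.

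**Conclusion.** The point holds as a free improvement. The Day 1 reference, the bedtime diary and the pre-dose baseline rule cannot all be followed for the same entry, and NRS30/NRS50 carry the conflict inside their own definitions. A 7-day pre-dose mean removes the ambiguity and is more precise than either single evening.

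Under the assumed ICC of 0.6 to 0.8 and level correlation of 0.4 to 0.6, change-score variance falls by about 13% to 27% with baseline averaging alone and by about 25% to 54% with averaging at both ends. At an ICC of 0.9 the both-ends gain is about 13% to 19%. None of these inputs comes from the documents. The size of any treatment effect on a Day 1 entry is unknown.

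The consequences are confined to the secondary pain endpoints, for which the protocol fixes only descriptive summaries and exact confidence intervals. The HiSCR analysis and the sample size are unaffected.

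**What to change.** In the SAP, before unblinding (Section 10.1 allows amendment up to that point):

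- Define the NRS baseline as the mean of the last 7 daily entries before first IMP, with a minimum number of entries (for example, 4). A minimum also tolerates a missed evening, which helps because Section 10.10 does not replace missing data for endpoints other than the primary.
- Define each time point as the mean of the 7 daily entries before the visit, with the same minimum. List the time points explicitly: a 7-day window before the Day 4 visit would reach back before the first infusion.
- Apply the threshold of 3 for NRS30 and NRS50 to this baseline, and count the reduction from the same value.
- Name the item, worst or average skin pain, used for each pain endpoint.
- Replace the Day 1 reference for these endpoints in Section 10.4.1, or state that the SAP definition governs.

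The cost is SAP wording and minor programming. The diary already collects the data.

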AE = adverse event, CRP = C-reactive protein, DLQI = Dermatology Life Quality Index, ECG = electrocardiogram, 5D-5L = EuroQol-5 Dimensions survey, FUV = follow-up visit, h = hour, HADS = Hospital Anxiety and Depression Scale, HBV = hepatitis B virus, HCV = hepatitis C virus, HiSCR = Hidradenitis Suppurativa Clinical Response, HIV = human immunodeficiency virus, HS = hidradenitis suppurativa, IMP = investigational medicinal product, min = minute, OV = optional visit, PK = pharmacokinetic(s), TNF = tumor necrosis factor, USV = unscheduled visit, V = visit, VxR= Visit for HiSCR responders, VxNR= Visit for HiSCR non-responders.

- (a) Update some inclusion/exclusion criteria, prior and concomitant therapy, and HS/medical history and surgery information to confirm subject eligibility.
- (b) All assessments intended to be performed at Week 44 should also be performed at early discontinuation visits. For subjects who discontinue early, a Post-Treatment Follow-Up visit will take place 3 months after early discontinuation or another HS therapy has been started, whichever occurs first. At the Post-Treatment Follow-Up visit the same parameters as at Week 44 will be assessed.
- (c) Blood samples must be obtained before IMP administration.
- (d) IMP administered according to dosing schedules in [Table 2](#) and [Table 3](#).
- (e) PK substudy in 8 to 10 subjects from each cohort. Blood samples will be obtained for analysis of IFX-1 in citrate plasma before IMP administration (0 h), after end of IMP administration (+ 10 min) and at 2 h ( $\pm$  10 min), 6 h ( $\pm$  10 min), 24 h ( $\pm$  2 h), and 48 h ( $\pm$  2 h) after start of IMP administration, in all cases using a separate infusion line.
- (f) Height and body weight will be assessed at Screening only.
- (g) Blood sample for IFX-1 analysis will be taken before IMP administration and directly after IMP infusion using a separate infusion line, with a time window of + 10 min.
- (h) Subjects will have a repeat ECG at Week 44 or at an early discontinuation visit if the subject discontinues before Week 44. If in the opinion of the investigator, clinically relevant AEs have developed during the study that warrant a repeat ECG examination this can be performed at any time during the study.
- (i) Blood sampling of serum and plasma biomarkers for future research is not applicable for Denmark.
- (j) Test only applicable for France.
- (k) Test only applicable for Denmark.

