### Extension Period (28 Weeks) – HiSCR Responders

Subjects from all cohorts who are HiSCR responders at Week 16 (response on the basis of HiSCR is defined in Section 8.2.2.2) will receive IFX-1 at a dose of 800 mg q4w, starting at Week 20 through Week 40. Subjects who have a loss of response (see [Definitions of Terms](#)) during the Extension Period will have an optional visit 2 weeks later. Subjects who then have a loss of response at the subsequent (planned) visit will be discontinued from the study.

A final visit at the study site for efficacy, PK, PD, and safety assessments will occur at Week 44. For subjects who discontinue early, a Post-Treatment Follow-Up visit will occur 3 months after the early discontinuation or when another HS therapy has been started, whichever occurs first. At the Post-Treatment Follow-Up visit the same parameters for efficacy, PK, PD and safety as at Week 44 or the early discontinuation visit will be assessed.

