### **6.2.2 Discontinuation of Treatment With Investigational Medicinal Product**

Subjects must be discontinued from treatment with the IMP under any of the following circumstances:

- Unacceptable toxicity or TEAE, as determined by the investigator
- Anaphylactic or other serious allergic reaction
- Serious infection, including meningitis and sepsis
- If, in the investigator's opinion, continued administration of IMP could be detrimental to the subject's well-being
- Use of prohibited treatment that in the opinion of the investigator or sponsor necessitates the subject being removed
- Application of lesion interventions exceeding the permitted number (see section [5.8.2.4](#))
- Biopsy confirmation of any malignancy
- Pregnancy
- Subjects who receive 800mg q4w and have a loss of response (see [Definition of Terms](#)) during the Extension Period will have an optional visit 2 weeks later. Subjects who still have a loss of response at the subsequent (planned) visit will be discontinued from the study and will not switch to the non-responder schedule
- Subjects who receive 800mg q2w and experience WOI (see [Definition of Terms](#)) at 2 consecutive visits in the Maintenance Period of the Extension Period will be discontinued from the study

Subjects who have been discontinued will have a Post-Treatment FUV 3 months after discontinuation or when another HS therapy has been started.

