### 8.2.2 Methods of Assessment

#### 8.2.2.1 Hidradenitis Suppurativa Clinical Parameters

To evaluate the severity of illness, the following HS clinical parameters will be assessed and documented at Screening, at Week 0 (Day 1), and at prespecified times during the study, as outlined in the [Schedules of Assessments](#) through Week 44 or an early discontinuation visit and the 3-month Post-Treatment Follow-Up visit, if the subject discontinues before Week 44:

- Affected area (i.e., left and right axilla, left and right sub/inframammary area, intermammary area, left and right buttock, left and right inguino-crural fold, perianal, perineal area, other [to be specified]), as described in guidance provided to the investigator

NOTE: lesions in each affected area will be counted. The identification of lesions will be performed according to standard definitions of elementary cutaneous lesions.

- 
- Number and type of lesions (i.e., abscesses, inflammatory nodules, non-inflammatory nodules, non-draining fistulas, draining fistulas, hypertrophic scars, other lesions [folliculitis, pustules])
  - Longest distance between 2 relevant lesions (mm)
  - Are lesions clearly separated by normal skin? (yes/no)

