## **10.10 Handling of Missing Data**

Data imputation rules are defined for missing values for the primary efficacy endpoint of percentage of subjects with a response, as measured by HiSCR at Week 16. Subjects with missing baseline assessments (baseline assessments might be obtained at Screening or at Day 1 before first infusion of IMP) necessary for the calculation of the HiSCR at Week 16 will not be randomized (i.e., there shall be no missing baseline values for HiSCR). Missing values for assessments at Week 16 necessary for the calculation of HiSCR at Week 16 will be replaced by multiple imputation, as described in section [10.5.1](#).

All other missing data will not be replaced.

Sensitivity analyses will be conducted based on the PPS. Further sensitivity analyses (e.g., evaluating patients with missing HiSCR at Week 16 as non-responders) will be defined in the statistical analysis plan if deemed necessary.

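### The Extension loss-of-response percentage keeps every Week 16 responder in the denominator but has no rule for those who leave without a recorded loss, so loss by Week 44 tends to be understated (minor)

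*Combined protocol and SAP*

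**What the plan says.** Section 10.4.1 adds one summary for the Extension Period to the by-time-point endpoints: the percentage of subjects with loss of response. Loss is "defined as a loss of at least 50% of the improvement (reduction) in the AN count achieved from baseline to Week 16", judged on the AN count alone, with no confirming visit required. The percentage is "based on the number of subjects with HiSCR at Week 16 will be analyzed for the Extension Period", so the denominator is fixed when the Extension starts.

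Section 10.10 defines imputation for HiSCR at Week 16 only, and then: "All other missing data will not be replaced". No section says how a responder who leaves the Extension with no recorded loss is to be classed.

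On withdrawal for loss, Section 6.2.2 states: "Subjects who still have a loss of response at the subsequent (planned) visit will be discontinued from the study". Lesion counts are scheduled when a subject leaves. Footnote (b) to the Schedules of Assessments says "All assessments intended to be performed at Week 44 should also be performed at early discontinuation visits", and Section 8.2.2.1 places the HS clinical parameters at "an early discontinuation visit and the 3-month Post-Treatment Follow-Up visit, if the subject discontinues before Week 44". Section 6.2 asks the investigator only to attempt the exit procedures. Nothing says whether exit or post-treatment counts feed the loss-of-response percentage.

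**The concern.** Responders can leave the Extension for reasons unrelated to a high AN count: adverse events, prohibited treatment, more than two omitted infusions, or withdrawal of consent. Under the stated rule these subjects remain in the denominator and cannot enter the numerator after they go. A responder who leaves at Week 22 with a low AN count is scored as free of loss for the remaining 22 weeks, during which nobody looked.

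Loss of response rests on AN, whereas HiSCR also requires no increase in abscesses or draining fistulas. A responder whose fistulas increase and who stops for lack of efficacy can therefore count as no loss. For the primary endpoint, Section 10.5.1 treats discontinuation for relapse, progression or lack of efficacy as non-response. There is no parallel rule here.

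This is the only endpoint defined specifically for loss of response, and it serves the secondary objective on long-term efficacy (Section 2.2). A reader will take the percentage as loss through Week 44, and the more subjects leave, the more favourable it looks.

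**Working it through.** **1. What the plan supplies.** There is no stated Extension loss or attrition rate to reproduce. Sections 3.2 and 10.2 give 5 × 35 = 175 randomised and 5 × 29 = 145 evaluable, an allowance of 30/175 = 17.1% over 16 weeks. The planning HiSCR rates of 25, 30, 45, 55 and 60% sum to 2.15. Expected Week 16 responders are therefore 29 × 2.15 = 62 to 35 × 2.15 = 75.

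**2. Assumptions.** L is the proportion who would lose response by Week 44 if all stayed: 30% or 40%. A is the proportion leaving for unrelated reasons over 28 weeks: 10%, 17% (the Main Period allowance) or 28% (the same weekly rate carried on, 1 − 0.83^(28/16) = 0.278). Hazards are constant and independent: λ = −ln(1−L) and μ = −ln(1−A) per 28 weeks.

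**3. AN fully observed up to exit.** Reported loss = λ/(λ+μ) × [1 − (1−L)(1−A)].
For L = 40%, A = 28%: 0.5108/(0.5108 + 0.3285) × (1 − 0.60 × 0.72) = 0.6086 × 0.568 = 34.57%.

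**4. No exit counts.** Responders have seven planned counts (Weeks 20, 24, …, 44). A loss registers only if the subject is still present at the next one. With s = (1−L)^(1/7) and r = (1−A)^(1/7), reported loss = (1−s) × r × [1 − (sr)^7]/(1 − sr).
For L = 40%, A = 28%: s = 0.92962, r = 0.95416, giving 0.07038 × 0.95416 × 0.568/0.11299 = 33.75%.

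| True loss | Attrition | Observed up to exit | Shortfall (points) | No exit counts | Shortfall (points) |
|---|---|---|---|---|---|
| 30% | 10% | 28.56% | 1.44 | 28.35% | 1.65 |
| 30% | 17% | 27.52% | 2.48 | 27.15% | 2.85 |
| 30% | 28% | 25.82% | 4.18 | 25.21% | 4.79 |
| 40% | 10% | 38.13% | 1.87 | 37.84% | 2.16 |
| 40% | 17% | 36.78% | 3.22 | 36.29% | 3.71 |
| 40% | 28% | 34.57% | 5.43 | 33.75% | 6.25 |

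**5. Kaplan-Meier on the same data.** At each visit, the proportion newly lost among those seen and not yet lost is 1 − s. The product over seven visits is s^7 = 1 − L, so the estimate returns the true 30% or 40%, provided the leavers are non-informative.

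**6. Scale.** With 62 responders, one standard error is sqrt(0.40 × 0.60/62) = 6.2 points or sqrt(0.30 × 0.70/62) = 5.8 points. The shortfall without exit counts runs from 1.65/5.8 = 0.3 to 6.25/6.2 = 1.0 standard error.

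**7. Timing and classing of leavers.** Suppose 15 of 75 responders leave before any Extension count, and 40% of the other 60 (24) lose response. The plan's rule gives 24/75 = 32.0%, evaluable-only gives 24/60 = 40.0%, and leavers counted as losses gives 39/75 = 52.0%. If all 15 have exit counts with the same 40% loss, every rule gives 30/75 = 40.0%.

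**The case against.** The case against has several parts.

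- **Exit data exist.** Lesion counts are due at the exit visit and again three months later. This narrows the gap but does not close it. Attendance is only attempted, use of the counts is not stated, and an exit count says nothing about the weeks after exit. If the three-month count were also used, everyone attended and the hazard were unchanged, a true 40% would be reported as 39.5, 39.1 or 38.5% at the three attrition levels. However, that visit follows the end of study treatment and can be triggered by the start of another HS therapy.
- **Much of the shortfall is a choice of estimand.** At a true 40%, losses that occurred before exit but went unseen come to only 0.3 to 0.8 points (step 3 minus step 4). The other 1.9 to 5.4 points are losses that would have followed had leavers stayed. This is correct. The plan does not say which quantity it intends, and a percentage over all responders for the whole Extension invites the second reading.
- **The attrition is borrowed.** The 17% is a Main Period allowance that includes placebo. Attrition among responders on active drug may be lower, hence the range.
- **Detail is deferred.** Section 10.1 leaves exact endpoint definitions to the statistical analysis plan. That is where a leaver rule belongs, but the denominator is already explicit in Section 10.4.1.
- **Low stakes.** HiSCR by time point is also summarised in the Extension by Week 16 responder status. This stands, and it limits the severity.

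Four stronger readings are tempting, and the documents do not support them.

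- **Every early leaver counts as having kept the response.** This is not so: "Subjects who then have a loss of response at the subsequent (planned) visit will be discontinued from the study", and such subjects met the AN definition before removal, so they are events.
- **The bias runs in one direction only.** No confirmation is required, so one transient AN rise counts as a loss. Section 5.8.2.4 also keeps any treated lesion in the count permanently.
- **The Week 44 figure would fall to about 5 to 9% because confirmed losers have been removed.** That needs a visit-by-visit display. Section 10.4.1 does say "The endpoints that are evaluated by time point will be analyzed in a similar way during the Extension Period", but it introduces the loss percentage separately, as one figure for the period.
- **Comparisons between randomised cohorts would be distorted.** All responders move to the same regimen, no test between cohorts is planned for this endpoint, and no cohort-specific attrition is given.

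**Conclusion.** The point holds in a limited form. Under the stated denominator and the no-replacement rule, a responder who leaves without a recorded loss is a non-event by default, and loss by Week 44 tends to be understated. The size is about 1.5 to 6 points without exit counts and 1.4 to 5.4 points with AN observed up to exit. Both ranges rest on assumed constant, independent hazards, a true loss of 30% to 40% and attrition of 10% to 28%, none of which the documents supply. Early clustering of departures would widen the gap, and unconfirmed AN rises could offset it. Severity is minor: the summary is descriptive and lies outside the primary and listed secondary endpoints. It is still worth changing, because a better estimate is available from data already scheduled for collection.

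**What to change.** In Section 10.4.1 and the statistical analysis plan:

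1. Report the Kaplan-Meier cumulative proportion with first loss of response, from Week 16, by Extension visit. A subject with a loss stays counted at all later visits, including after withdrawal.
2. State that the AN count from the early discontinuation visit is used, and at what time it is placed. Censor other leavers at their last lesion count.
3. Keep the crude percentage of all Week 16 responders as a supplementary row.
4. Add a sensitivity analysis that counts discontinuation for lack of efficacy, relapse or progression as a loss, in line with the primary-endpoint rule in Section 10.5.1. It belongs in a sensitivity analysis because it goes beyond the AN definition.
5. Say whether a single AN rise is enough or a confirmed loss is needed. Section 7.3 ties withdrawal to loss at the optional visit, while Sections 3.1, 5.4.2 and 6.2.2 tie it to the subsequent planned visit. These passages must be reconciled before a confirmed loss can be defined.

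The cost is SAP wording and one extra table, with no new data. The downside is that Kaplan-Meier assumes the censored leavers are non-informative, which the sensitivity analysis in item 4 partly probes.
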